6.0 Registration Procedures

- 6.1 Site Procedures
 - 6.11 Study staff will need to complete the required training prior to gaining access to the registration application. This is located on the ACCRU web page at

 Refer to Study Resources → Applications. Near the bottom of the page there will be a link to the "Research Registration Application Training." After training is complete, study staff must complete the "Attestation of Training" and send to the ACCRU Registration Office at
 - 6.12 Documentation of IRB approval must be on file in the Registration Office before an investigator may register any patients. Approvals should be uploaded using the online ACCRU Regulatory Management System (ARMS).

In addition to submitting initial IRB approval documents, ongoing IRB approval documentation must be on file (no less than annually) with ACCRU. Approvals should be uploaded using the online ACCRU Regulatory Management System (ARMS). If the necessary documentation is not submitted in advance of attempting patient registration, the randomization will not be accepted and the patient may not be enrolled in the protocol until the situation is resolved.

Submission of annual IRB approvals is required until the study has been closed through your IRB.

6.2 Safety Portion

Prior to discussing protocol entry with the patient, call the ACCRU Registration Office to ensure that a place on the protocol is open to the patient.

- 6.21 To register a patient, fax a completed eligibility checklist to the Academic and Community Cancer Research United (ACCRU) Registration Office between 8 a.m. and 4:30 p.m. central time Monday through Friday.
- 6.3 Expansion Portion

6.31 To register a patient, access the ACCRU web page at go to the Study Resources → Application section and click on "Registration" and enter the registration application. The registration application is available 24 hours a day, 7 days a week. Back up and/or system support contact information is available on the Web site. If unable to access the Web site, call the Academic and Community Cancer Research United (ACCRU) Registration Office at between the hours of 8 a.m. and 4:30 p.m. Central Time (Monday through Friday).

Instructions for the registration application are available on the above web page under the Study Resources → Application section. Please refer to the "Research Registration Application Training" or Quick Reference Guide for instructions.

Prior to initiation of protocol study intervention, this process must be completed in its entirety and a ACCRU subject ID number must be available as noted in the instructions. It is the responsibility of the individual and institution registering the patient to confirm the process has been successfully completed prior to release of the study agent. Patient registration via the registration application can be confirmed in any of the following ways:

- Contact the ACCRU Registration Office If the patient was fully registered, the ACCRU Registration Office staff can access the information from the centralized database and confirm the registration.
- Refer to the Research Registration Application training on the ACCRU website under Study Resources → Applications.
- 6.4 Safety and Expansion Portions
 - 6.41 Correlative Research

A mandatory correlative research component is part of this study, the patient will be automatically registered onto this component (see Sections 3.19a, and 17.1).

An optional correlative research component is part of this study, there will be an option to select if the patient is to be registered onto this component (see Sections 14.1 and 17.1).

- Patient has/has not given permission to give his/her blood sample for research testing.
- Patient has/has not given permission to give his/her tissue sample for research testing.
- 6.42 Prior to accepting the registration, registration application will verify the following:
 - IRB approval at the registering institution
 - Patient eligibility
 - Existence of a signed consent form
 - Existence of a signed authorization for use and disclosure of protected health information
- 6.43 At the time of registration, the following will be recorded:
 - Patient has/has not given permission to store and use his/her blood sample(s)

- for future research to learn about, prevent, or treat cancer.
- Patient has/has not given permission to store and use his/her blood sample(s) for future research to learn, prevent, or treat other health problems (for example: diabetes, Alzheimer's disease, or heart disease).
- Patient has/has not given permission to store and use his/her tissue sample(s) for future research to learn about, prevent, or treat cancer.
- Patient has/has not given permission to store and use his/her tissue sample(s) for future research to learn, prevent, or treat other health problems (for example: diabetes, Alzheimer's disease, or heart disease).
- Patient has/has not given permission for ACCRU to give his/her sample(s) to outside researchers.
- 6.44 Treatment cannot begin prior to registration and must begin \leq 21 days after registration.
- 6.45 Pretreatment tests/procedures (see Section 4.0) must be completed within guidelines specified on the test schedule.
- 6.46 All required baseline symptoms (see Section 10.52) must be documented and graded.
- 6.47 Treatment on this protocol must commence at an ACCRU institution under the supervision of a medical oncologist or hematologist.
- 6.48 Blood draw kit is available on site.

7.0 **Protocol Treatment**

Safety Portion: An initial 6 patients will receive rituximab via IV on day 1 of cycle 1. On day 1 of cycles 2-6 patients will receive rituximab and hyaluronidase human subcutaneously. On day 1 of cycles 1-6 patients will receive polatuzumab vedotin via IV. Patients will also receive venetoclax daily during all cycles. See Table 7.2 for details.

Expansion Portion: After confirming the optimal and safe tolerable dose of venetoclax, patients will continue with the same schedule of rituximab and hyaluronidase human. The safety portion will determine the frequency of venetoclax dosage.

7.1 Treatment Schedule - Use actual weight or estimated dry weight if fluid retention Pretreatment medication

Agent	Dose	Route	Day
Dexamethasone ¹	10-20 mg	IV or PO	Within 1 hour of R/ScHyc/Pola
Acetaminophen ¹	650mg	PO	Within 1 hour of R/ScHyc/Pola
Benadryl ¹ and	25-50 mg		
Ranitidine or	50 mg	IV^2	30 minutes prior to R/ScHyc/Pola
Cimetidine or	300 mg		
Famotidine	20 mg		
Allopurinol	100mg	PO	Three times daily from day 1 of cycle 1 to day 1 of cycle 3.

Acyclovir	400mg	PO	Twice daily
Bactrim DS	1 tablet three times a week	oral	Continuously during treatment. Monday/Wednesday/Friday

- 1. If taken within 8 hours of Rituximab and polatuzumab, each premedication will only need to be taken once per cycle
- 2. Benadryl can be taken PO or IV

7.2 Induction (Cycles 1-6):

- Patients will receive rituximab 375mg/m² IV on day 1 of cycle 1, and rituximab and hyaluronidase human SQ day 1 of cycles 2-6
- Patients will receive polatuzumab vedotin 1.8 mg/kg IV on Day 1 of each 21-day cycle for a total of 6 cycles.
- Patients will receive venetoclax PO 20 mg beginning on day 1 of cycle 1. On day 7 of cycle 1 they will begin ramp-up increasing over 5 weeks to 400 mg po daily days 1-21 cycles 1-6. If not tolerated venetoclax will be dose reduced.
- Missed/skipped/vomited doses will not be made up (i.e. the patient should not double their dose if the previous dose was missed).
- For first infusion only, vital signs to be collected prior to dosing, every 15 minutes (+/- 5 minutes) during dosing and 30 minutes (+/- 10 minutes) after treatment completion until vital signs normalize or return to baseline. For vital signs that are normal/return to baseline at the 30 minutes (+/-10 minutes) assessment, no additional vitals are required. For subsequent infusions, vital signs should be collected prior to dosing and every 30 minutes (+/- 10 minutes) during dosing. After treatment completion: Patients who have never had a documented infusion reaction, post-dosing vital signs may be obtained at 30 minutes post infusion for the second infusion, and thereafter at 15 minutes aftertreatment completion. Additionally, O2 should be monitored as a vital sign during each visit. In cycle 1, if the investigator feels that the patient is at significant risk of tumor lysis, patients should be monitored for tumor lysis per institutional standard.
- When study treatments are given on the same day, they will be administered sequentially in the following order:

Order of Administration (See section 15 for individual drug instructions)

- 1) Venetoclax[#] (No time constraints)

- 1. Since cycle length is 30 days, rituximab and hyaluronidase human maintenance is given once every other cycle. A total of 6 rituximab and hyaluronidase human treatments during the maintenance phase.
- 2. A +/- 7 day window is allowed for day 1 of treatment during maintenance. NOTE: No polatuzumab vedotin will be administered.
- 3. All subjects who get a dose reduction of Venetoclax during induction, will be maintained on the same corresponding dose in maintenance.
 - * If 400 mg days 1-21 is not tolerated in the *safety run-in*, venetoclax will be given 400 mg days 1-10.
- 4. For Venetoclax dose reductions in Maintenance refer to Table 8.21.
- 7.4 For this protocol, the patient must return to the consenting ACCRU institution for CBC evaluation, or have outside laboratory CBC every 7 days during the first 6 weeks of therapy, every 30 days during maintenance, and every 3 months during clinical follow-up (Active Monitoring Phase).

- 7.5 Study treatment by a local medical doctor (LMD) is not allowed.
- 7.6 Safety Portion: Rules for Dose De-escalation

Dose de-escalation will be considered if the initial safety portion dose level (venetoclax 400 mg days 1-21) per Table 7.2a proves excessively toxic, with 2 or more subjects having excessive significant toxicity as defined in Section 7.7. Dose de-escalation will proceed per section 7.6.1.

7.61 The first cohort of three patients will be treated at the starting dose level of Venetoclax (400 mg days 1-21) and observed for at least 63 days (3 cycles) from the start of treatment to assess toxicity. If significant toxicity as defined in Section 7.7 is observed in 0 or 1 of these 3 patients, 3 new patients will be accrued and treated at same dose level of Venetoclax (400 mg days 1-21) and observed for 3 cycles. After enrolling 6 patients on Venetoclax dose level of 400 mg days 1-21, if ≤1 patient experience significant toxicity, then this dose will be considered safe and the rest of the patients in expansion cohort will be treated at this dose level of Venetoclax. However, if 2 or more out of the first 3 or 6 patients experience significant toxicity, then the dose of venetoclax may be descalated to 300mg days 1-21. In this case, another safety analysis using similar 3+3 design approach will be conducted at the reduced dose level of venetoclax.

7.7 Definitions of significant toxicity

- 7.71 Toxicity will be measured per NCI-CTCAE version 5. For this protocol, significant toxicity will be defined as an adverse event occurring during the first 3 cycles of treatment that is possibly, probably, or definitely related as follows: NOTE: All significant non-hematologic toxicities must be resolved to a minimum of grade 1 for ongoing treatment at any cycle of treatment.
 - 7.711 Non-Hematological significant toxicities. Any Grade 3 or Grade 4 non-hematological toxicity that is possibly, probably or definitely attributable to the regimen of RSC+Pola+Ven is considered a significant toxicity, including the following:
 - Non-hematologic toxicity that causes a delay of >14 days in initiating cycle 2.
 - Any type of grade 3-4 hypersensitivity reaction (i.e.: allergic reaction, anaphylaxis, serum sickness, skin disorders, etc.), regardless of attribution, that necessitate discontinuation of study drug.
 - Any type of grade 3-4 immune related adverse event or immune system disorder including skin reactions.
 - Grade 3 or greater colitis and bowel perforation
 - Grade 3 ALT/AST elevation
 - Grade 3 or greater TLS

NOTE: The following events are exclusions and are NOT considered a significant toxicity for this protocol, regardless of attribution or specific type:

• Grade 3 nausea, vomiting, diarrhea, or oral mucositis with < 3 days

duration.

- Grade 3 fever.
- Grade 3 peripheral sensory neuropathy that is decreased by at least one grade within 7 days.
- Grade 3 hypophosphatemia, hypokalemia, hypocalcemia or hypomagnesemia responsive (i.e.: decreased by at least one grade) to oral supplementation within 7 days.
- Grade 3 hypertriglyceridemia that returns to < Grade 2 prior to the beginning of cycle 2.
- Grade 3 hyperglycemia that returns to < Grade 2 (with or without the use of insulin or oral diabetic agents) prior to the beginning of cycle 2.
- 7.713 Hematological significant toxicity. The following hematological toxicity possibly, probably or definitely attributable to the regimen of RSC+Pola+Ven is considered a significant toxicity:
 - Grade 4 neutropenia for > 7 days without growth factor support
 - Grade 4 febrile neutropenia
 - **NOTE:** Grade 4 non-febrile neutropenia will not be a significant toxicity but should warrant growth factor support on subsequent doses.
 - Platelet count < 25,000/uL on 2 separate days, or requiring a platelet transfusion on 2 separate days within a 7-day period
 - Myelosuppression that causes a delay of > 14 days in initiating cycle 2
 - Grade 3 thrombocytopenia with grade > 2 bleeding

NOTE: Growth factors are allowed per treating investigator's discretion in patients at high risk for febrile neutropenia after cycle 2, or in a patient who has demonstrated neutropenia on previous doses. Patients who are otherwise eligible per protocol with demonstrated bone marrow infiltration, may be treated with prophylactic growth factor support.

7.8 Patients will be required to keep a medication diary for venetoclax using the diary in Appendix V. Sites will be required to upload medication diary to RAVE at the end of each cycle.

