8.3 Toxicities during Induction Treatment

Table 8.31: Guidelines for Management of Hematologic Toxicities That Occur During Induction Treatment.

Heatment.					
Event	Action to Be Taken				
Grade 3 or	For patients who have had one or no prior venetoclax or polatuzumab vedotin				
4	dose reduction:				
Hematogic	• Withhold study treatment. ¹				
Toxicity ¹	 Administer RBCs or platelets as required. 				
	 If patient has not already initiated G-CSF, initiate prophylactic G-CSF for current and subsequent cycles. 				
	 Resume venetoclax and polatuzumab vedotin at same dose after interruption for 1st occurrence, once the toxicity has resolved to Grade 1 or baseline level 				
	 Resume venetoclax and polatuzumab vedotin at one level dose reduction after interruption for 2nd occurrence, once the toxicity has resolved to Grade 1 or baseline level. Refer to table 8.21 for dose reduction steps. 				
	• For patients who develop platelet count of 20,000/L while receiving LMWH, reduce the dose of LMWH. For patients who develop platelet count of 20,000/L while receiving platelet inhibitors, consider temporarily withholding platelet inhibitors.				
	No more than 2 dose level reductions in venetoclax and				
	polatuzumab vedotin are allowed during induction.				
	 Consider discontinuation of study drug for patients who require withholding study drug for more than 21 days. 				
	For patients who have had two prior venetoclax dose reductions:				
	 Permanently discontinue study treatment. 				
	 For grade 4 thrombocytopenia ≥ 7 days or grade 3 thrombocytopenia with ≥ grade 2 bleeding resume venetoclax and polatuzumab at one dose level dose reduction after the toxicity has resolved to Grade 1 or baseline level 				

(G-CSF) granulocyte colony-stimulating factor; (LMWH) low molecular weight heparin.

¹ Treatment delays apply to all toxicities; dose modifications apply only to toxicities that are considered to be related to any of the study treatment components. Toxicities that occur during the cycle and subside prior to the next cycle should not trigger the suggested dose modifications.

Table 8.32: Guidelines for Management of Non-Hematologic Toxicities That Occur During Induction

Table 8.32: Guide	elines for Management of Non-Hematologic Toxicities That Occur During Induction		
Event	Action to Be Taken		

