8.5 Management of Adverse Reactions for polatuzumab

Table 8.51 Management of Peripheral Neuropathy, Infusion-Related Reaction, and Myelosuppression

Table 8.51 Management of	Table 8.51 Management of Peripheral Neuropathy, Infusion-Related Reaction, and Myelosuppression				
Event	Dose Modification				
Grade 2–3 Peripheral Neuropathy	 Hold polatuzumab dosing until improvement to Grade 1 or lower. If recovered to Grade 1 or lower on or before Day 14, restart polatuzumab with the next cycle at a permanently reduced dose of 1.4 mg/kg. If a prior dose reduction to 1.4 mg/kg has occurred, discontinue polatuzumab. If not recovered to Grade 1 or lower on or before Day 14, discontinue polatuzumab. 				
Grade 4 Peripheral Neuropathy	Discontinue polatuzumab.				
Grade 1–3 Infusion- Related Reaction	 Interrupt polatuzumab infusion and give supportive treatment. For the first instance of Grade 3 wheezing, bronchospasm, or generalized urticaria, permanently discontinue polatuzumab. For recurrent Grade 2 wheezing or urticaria, or for recurrence of any Grade 3 symptoms, permanently discontinue polatuzumab. Otherwise, upon complete resolution of symptoms, infusion may be resumed at 50% of the rate achieved prior to interruption. In the absence of infusion related symptoms, the rate of infusion may be escalated in increments of 50 mg/hour every 30 minutes. For the next cycle, infuse polatuzumab over 90 minutes. If no infusion-related reaction occurs, subsequent infusions may be administered over 30 minutes. Administer premedication for all cycles. 				
Grade 4 Infusion- Related Reaction	 Stop polatuzumab infusion immediately. Give supportive treatment. Permanently discontinue polatuzumab. 				
Grade 3–4 Neutropenia ^{a,b}	 Hold all treatment until ANC recovers to greater than 1000/microliter. If ANC recovers to greater than 1000/microliter on or before Day 7, resume all treatment without any additional dose reductions. Consider granulocyte colony-stimulating factor prophylaxis for subsequent cycles, if not previously given. 				
Grade 3–4 Thrombocytopenia ^{a,b}	 Hold all treatment until platelets recover to greater than 75,000/microliter. If platelets recover to greater than 75,000/microliter on or before Day 7, resume all treatment without any additional dose reductions. 				
Infections and Infestations: Hepatitis Viral	Discontinue therapy and treat hepatitis				

^a Severity on Day 1 of any cycle.

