9.0 Ancillary Treatment/Supportive Care

- 9.1 Antiemetic's may be used at the discretion of the attending physician.
- 9.2 Blood products and growth factors should be utilized as clinically warranted and

^b If primary cause is due to lymphoma, dose delay or reduction may not be needed.

following institutional policies and recommendations. The use of growth factors should follow published guidelines of the American Society of Clinical Oncology (ASCO), Recommendations for the Use of WBC Growth Factors: American Society of Clinical Oncology Clinical Practice Guideline Update. J Clin Oncol 2015;33:3199-3212.

- 9.3 Patients should receive full supportive care while on this study. This includes blood product support, antibiotic treatment, and treatment of other newly diagnosed or concurrent medical conditions. All blood products and concomitant medications such as antidiarrheals, analgesics, and/or antiemetics received from the first day of study treatment administration until 30 days after the final dose will be recorded in the medical records.
- 9.4 Diarrhea: This could be managed conservatively with loperamide. The recommended dose of loperamide is 4 mg at first onset, followed by 2 mg every 2-4 hours until diarrhea free (maximum 16 mg/day).

In the event of grade 3 or 4 diarrhea, the following supportive measures are allowed: hydration, octreotide, and antidiarrheals.

If diarrhea is severe (requiring intravenous rehydration) and/or associated with fever or severe neutropenia (grade 3 or 4), broad-spectrum antibiotics must be prescribed. Patients with severe diarrhea or any diarrhea associated with severe nausea or vomiting should be hospitalized for intravenous hydration and correction of electrolyte imbalances.

- 9.5 Carriers of hepatitis B virus (HBV) should be closely monitored for clinical and laboratory signs of active HBV infection and for signs of hepatitis during and for up to several months following Rituxan therapy. In patients who develop viral hepatitis, Rituxan and any concomitant chemotherapy should be discontinued and appropriate treatment, including antiviral therapy, initiated. There are insufficient data regarding the safety of resuming Rituxan therapy in patients who develop hepatitis subsequent to HBV reactivation.
- 9.6 Prohibited Medications or Therapies
 - 9.61 CYP3A Inhibitors/Inducers

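### The run-in counts toxicity for 63 days, but cycle 3 has one scheduled blood count and the neutropenia wording leaves open which prolonged Grade 4 episodes count

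*Combined protocol and SAP*

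**What the plan says.** **Dose rule.** Under Sections 7.61 and 16.4, three and then three more patients start at venetoclax 400 mg and are each observed for at least 63 days. With at most 1 of 6 having significant toxicity, 400 mg goes forward to the expansion. With 2 or more, the dose may drop to 300 mg.

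**Event definition.** Section 7.713 lists "Grade 4 neutropenia for > 7 days without growth factor support". A NOTE shortly below it says: "Grade 4 non-febrile neutropenia will not be a significant toxicity but should warrant growth factor support on subsequent doses".

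**Growth factors.** The note closing Section 7.7 leaves them to the investigator's "discretion in patients at high risk for febrile neutropenia after cycle 2", or after neutropenia on earlier doses, and adds: "Patients who are otherwise eligible per protocol with demonstrated bone marrow infiltration, may be treated with prophylactic growth factor support". Table 8.31, for Grade 3 or 4 hematologic toxicity in induction, says: "If patient has not already initiated G-CSF, initiate prophylactic G-CSF for current and subsequent cycles". Table 8.51 says: "Consider granulocyte colony-stimulating factor prophylaxis for subsequent cycles, if not previously given"; its footnote a ties the grade to "Severity on Day 1 of any cycle". Section 9.2 adds: "Blood products and growth factors should be utilized as clinically warranted".

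**Blood counts.** Section 7.4 and footnote 18 of the test schedule (Section 4.0) require a CBC every 7 days for six weeks. The schedule column for cycles 3 to 6 marks day 1 only. Table 7.2b starts 400 mg in cycle 2, week 2.

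**The concern.** A toxicity criterion with a duration threshold needs counts close enough together to show the event, and wording that classifies it the same way everywhere. Weekly counts stop just as patients enter their one complete cycle at the dose being tested. The definition also leaves two questions open: whether the NOTE overrides the bullet above it, and whether G-CSF should already have been started when the episode passes day 7. With six patients and a limit of one event, a single missed or reclassified patient can change the dose taken into the expansion.

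**Working it through.** **1. Window.** 3 cycles × 21 days = 63 days, which reproduces the figure in Sections 7.61 and 16.4.

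**2. Time at 400 mg.** On an on-time ramp-up, cycle 2 week 2 starts on day 21 + 7 + 1 = 29.
- Window days at 400 mg: 63 − 29 + 1 = 35.
- Of these, under weekly CBCs (to day 6 × 7 = 42): 42 − 29 + 1 = 14.
- In cycle 3: 63 − 42 = 21, which is 21/35 = 60%.

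**3. Scheduled counts.** The schedule gives about days 1, 8, 15, 22, 29, 36, 43 (cycle 3 day 1) and 64 (cycle 4 day 1). Appendix III adds hematology around each ramp-up step, with a 24-hour sample on about days 2, 9, 16, 23 and 30. The last of these follows the first 400 mg dose, so an on-time ramp-up adds nothing after day 30. Days 44 to 63 are 20 days without a scheduled count.

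**4. Detection.** A Grade 4 episode of L days lying wholly in days 44 to 63 has 21 − L possible start days. For every L from 8 to 20, the number of scheduled counts inside the episode is 0. Adding days 50 and 57 leaves uncovered runs of 6 days (44–49, 51–56, 58–63), so every episode of 8 days or more gets at least one reading.

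Length is harder to show. Two readings 7 days apart span 8 days counted inclusively, and both fall inside the episode only if it starts by day 50 and lasts to day 57:

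| L (days) | Start days giving both readings | Share |
|---|---|---|
| 8 | 1 of 13 | 8% |
| 10 | 3 of 11 | 27% |
| 14 | 7 of 7 | 100% |

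Repeat counts after a Grade 4 result are therefore needed as well.

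**5. Definition, side by side.** Take a hypothetical non-febrile Grade 4 episode on days 29 to 38 (10 days).

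| Reading | G-CSF during the episode | Counted? |
|---|---|---|
| Table 8.31 (current cycle) | Yes | No, because supported |
| 7.713 NOTE or Table 8.51 (later doses or cycles), NOTE read as 7 days or less | No | Yes |
| Same, NOTE read literally | No | No |

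The patient is the same in all three rows. The answer depends on which instruction the site follows and how it reads the NOTE.

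**6. Effect on the dose decision (assumed rates only).** Passing means at most 1 of 6: (1 − p)^6 + 6p(1 − p)^5. Let q be the rate of other significant toxicity and g the rate of uncomplicated prolonged Grade 4 neutropenia. If independent, p = 1 − (1 − q)(1 − g) when the event is always counted, and p = q when it never is.

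| q | g | p if counted | Pass, never counted | Pass, always counted |
|---|---|---|---|---|
| 10% | 5% | 0.145 | 0.886 | 0.788 |
| 10% | 10% | 0.190 | 0.886 | 0.680 |
| 20% | 5% | 0.240 | 0.655 | 0.558 |
| 20% | 10% | 0.280 | 0.655 | 0.464 |

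The largest difference is 0.886 − 0.680 = 0.206. It is 0 if the events fall only in patients who already have another significant toxicity. Never against always is an outer bound at these rates; the cycle 3 gap alone would account for only part of it.

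**The case against.** The strongest reply is that the criterion works for most purposes.

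- **Growth factor clause.** Counting only unsupported episodes can be read as a deliberate choice that prolonged neutropenia managed with G-CSF does not limit dose. That stands. It does not settle when G-CSF should start, which decides who falls under the clause.
- **The NOTE.** It follows the febrile neutropenia bullet, and reading it to erase the more-than-7-days bullet would leave that bullet without meaning. The narrow reading is the sensible one, but it is not written down.
- **Follow-up of seen events.** Table 8.31 withholds treatment until recovery to Grade 1 or baseline, and Table 8.51 until ANC exceeds 1000/microliter. Neither can be followed without repeat counts. This helps once a low count has been seen. It does nothing for an episode that starts after day 43 and resolves before day 64.
- **Other safeguards.** Grade 4 febrile neutropenia, related Grade 3–4 infection and a delay of cycle 2 beyond 14 days still count. Section 10.53 collects Grade 3–4 events whatever their attribution, and Sections 16.51 and 16.52 allow discretionary action. These stand, so what can be missed is mainly the uncomplicated episode. The hematologic rules in 16.522 count only patients who discontinue.

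Two stronger readings are tempting. One is that the criterion cannot be met. The documents do not support that: in cycles 1 and 2, a patient whose site follows the later-dose instructions can meet it on the narrow reading of the NOTE. The other is that the platelet criterion fails in the same way. Its two low counts need not both fall in cycle 3; days 36 and 43 would serve, and transfusions are an alternative route.

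**Conclusion.** The concern holds in two limited parts. First, a Grade 4 neutropenia episode of 8 to 20 days within about days 44 to 63, without complications, is on no scheduled count. This follows from the schedule, assuming cycles and ramp-up run on time and no unscheduled CBC is drawn; a ramp-up step delayed into cycle 3 would bring its own samples. Second, the NOTE conflicts with the bullet as written, and the differing G-CSF timings make classification depend on the site.

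A reader might infer a loss of up to 21 percentage points in the chance of clearing 400 mg. The documents do not support a figure, because no rate for prolonged Grade 4 neutropenia with this triplet is given. The nearest data are Grade 4 neutropenia DLTs, with no duration stated: 1 of 10 and 1 of 9 patients at polatuzumab 2.4 mg/kg (1.8 mg/kg here), and 1 of 10 in the venetoclax 600 mg cohort, with no DLTs in later cohorts up to 1200 mg. Sections 1.332 and 1.4 are also reassuring about related combinations. The direction is clear and the size is not. This is a cheap improvement to the data that set the expansion dose.

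**What to change.** 1. In Section 7.4 and test-schedule footnote 18, continue weekly CBCs through day 63 for run-in patients (about days 50 and 57). After any Grade 4 ANC, repeat the count, for example every 2 to 3 days, until it is no longer Grade 4.
2. Limit the 7.713 NOTE to non-febrile Grade 4 neutropenia of 7 days or less.
3. State one G-CSF timing rule for run-in patients, and use it in 7.713, the note closing 7.7, and Tables 8.31 and 8.51.

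Whether G-CSF-supported episodes of more than 7 days should count is the sponsor's choice. Counting them is stricter and makes de-escalation more likely.

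**Cost.** Wording changes, 2 × 6 = 12 extra CBCs (the same again if a second run-in of six opens at 300 mg), and a few repeat counts in any patient with a Grade 4 result. The chance of de-escalation rises somewhat, by an amount that the documents cannot fix.
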